1	
2	
4	
5	
6	
7	
8	
9	
10	
12	
13	
14	
15	
16	
17 19	
10	
20	
21	
22	
23	
24	RESEARCH PROTOCOL - Use of the eFisioTrack system for monitoring prescribed
25	therapeutic exercises in patients with shoulder orthopedic injuries in a hospital setting: A
26	pilot feasibility study
27	
28	18/07/2023
29	
30	
31	
32 33	
33 34	
35	
36	
37	
38	
39	
40 41	
42	
43	
44	
45	
46	
4/ /9	
44	

1

RESEARCH PROTOCOL - Use of the eFisioTrack system for monitoring prescribed
 therapeutic exercises in patients with shoulder orthopedic injuries in a hospital setting: A
 pilot feasibility study

5 6

PROJECT SUMMARY

7 8 **Rationale**

9 To assess the effects of the eFisioTrack monitoring system on clinical variables in patients
 10 with prescribed physiotherapy for shoulder injuries.

1112 Objectives

The main aim of the study was to evaluate the effect on clinical variables of monitoring exercises prescribed for shoulder injury rehabilitation with the eFisioTrack platform in patients of the Rehabilitation Service at University Hospital of Elche.

16

17 Methods

18 A pilot feasibility study, single bling with two groups (experimental and control group).

- 19 Clinical outcome measures will be shoulder function and pain (Constant Murley Score
- 20 and Disabilities of the Arm, Shoulder, and Hand or DASH score). Each variable will be
- 21 measured by a blinded physiotherapist at baseline and at one month follow-up. Patients
- 22 performed the prescribed exercises either supervised by the physiotherapist (control
- 23 group) or in a separate room without therapist supervision (experimental group).

24

25 **Population**

The study will be carried out in the buildings of the Rehabilitation Service at University Hospital of Elche, starting in July 2023 and finishing in December 2023.

28

29 Expected outcomes.

This study aims to contribute to the advancement of the knowledge about the shoulder treatment. The system shows promising results as a work item in shoulder home-based rehabilitation. In fact, real-time telerehabilitation is a strategy for interventions in other musculoskeletal conditions, to provide continuity to healthcare services and mitigate distance and displacements. Confirmation of these preliminary results could reduce the workload of physiotherapy services, contributing to resource efficiency.

36

9 RATIONALE AND BACKGROUND INFORMATION

10 Shoulder pain is a common health problem, and its prevalence has been estimated at 11 around 7%–26%. There are several conditions that can produce pain in the shoulder 12 complex, such as fractures, frozen shoulder, rotator cuff tendinopathy, or subacromial 13 syndrome. Physiotherapy management helps to reduce pain, improve range of movement 14 and strength, and improve function. Combining active exercises with manual therapies is 15 a common practice when treating musculoskeletal injuries of the shoulder.

16 Therapeutic exercise, in both the physical therapy setting and at home, is a fundamental 17 component of shoulder rehabilitation plans whether treatment is performed with or 18 without surgery, and there is evidence of its effectiveness in the management of shoulder 19 conditions⁵. The primary goal of a shoulder exercise program is to relieve pain, increase 20 strength, reduce muscle imbalances, and restore pain-free joint range of motion. 21 Therefore, its correct execution is of great importance for the clinical course.

However, one of the main problems in orthopedic shoulder rehabilitation is poor adherence to home exercise prescriptions. Some strategies for their control, such as daily or video recording, have been described, but their use is limited by recall bias or the need for advanced technology.

26 There is a growing number of trials about the use of technology to monitor rehabilitation 27 exercises. Its application in shoulder injuries could be potentially beneficial. Carbonaro et al. presented the development and preliminary testing of a wearable-technology 28 29 platform for the remote rehabilitation of shoulder muscular-skeletal diseases. This system 30 (Shoulphy) was designed to lead and assess the patient wearing a minimal set of inertial sensors and following personalized physical rehabilitation programs under the remote 31 supervision of the physician/therapist. Pan et al. reported the use of accelerometer-based 32 33 sensors built into a smartphone to capture the rehabilitation exercises as a self-home monitoring system. Wearable sensors, smartphones, and inertial measurement units have 34 35 become a feasible option for monitoring joint movement. There is also research on the application of Nintendo® Wii-technology for monitoring therapeutic exercises on 36 shoulder injuries¹⁶. This is based on accelerometers and gyroscopes located in the 37 38 controls, making it a low-cost option. However, most of these focus on stroke, to improve 39 arm function and balance in hemiparetic patients

Ruiz-Fernandez et al. described a software platform based on Wii-controls technology that could be used to monitor patients' activity in the scheduled exercise sessions. However, there is no clinical study of the results obtained in the laboratory. Therefore, the aim of this pilot study was to evaluate the effect on clinical variables of monitoring exercises prescribed for shoulder injury rehabilitation with the eFisioTrack platform in patients of the Rehabilitation Service at University Hospital of Elche. 1

2 OBJECTIVES

The main aim of the study was to evaluate the effect on clinical variables of monitoring exercises prescribed for shoulder injury rehabilitation with the eFisioTrack platform in patients of the Rehabilitation Service at University Hospital of Elche.

6

7 STUDY DESIGN

8 A pilot feasibility study, single bling with two groups (experimental and control group). 9 Clinical outcome measures will be shoulder function and pain (Constant Murley Score 10 and Disabilities of the Arm, Shoulder, and Hand or DASH score). Each variable will be 11 measured by a blinded physiotherapist at baseline and at one month follow-up. Patients 12 performed the prescribed exercises either supervised by the physiotherapist (control 13 group) or in a separate room without therapist supervision (experimental group).

14

15 **Regarding the study population**.

16 Patients who will be referred to the rehabilitation service of the University Hospital of

17 Elche (Spain) for physiotherapy treatment (manual therapy, exercise, stretching, and

18 electrotherapy) after suffering orthopedic injury or surgery in the shoulder joint complex,

19 from July 2023 to December 2023 will be considered for enrollment in the study.

20 Inclusion criteria were established as follows:

- 21 (i) be at least 18 years old and be able to read and understand Spanish.
- 22 (ii) suffer a traumatic or degenerative shoulder injury, with or without surgical
 23 treatment.
- (iii) have a prescription for rehabilitative physical therapy that includes active exercises.
- 26

27 The exclusion criteria adopted were:

Patients were excluded if they had a concomitant injury on an upper extremity or the cervical spine at the time of participation or sequelae of previous injuries in the area.

30

31 Regarding sample size

The main objective of this study is to know whether a clinical trial will be feasible and to have an estimate of standard deviation, which will be used in the sample size calculation for the large-scale trial; to estimate the rate (proportion) of eligible people who are willing to participate, of participants who drop out of the trial, or of participants who comply with the assigned intervention. That is why the sample size could be between 20 and 40 participants.

38

39 **METHODOLOGY**

40 Following baseline examination, patients will be randomly assigned to either 41 physiotherapist-supervised exercise (control group) or monitoring by the eFisioTrack

system (experimental group). Patients will perform the prescribed exercises either 1 2 supervised by the physiotherapist (control group) or in a separate room without therapist 3 supervision (experimental group). A system of codes (four last numbers of the patient's ID number) was assigned to each participant using a computerized application (Research 4 randomizer: www.randomizer.org). Clinical outcome measures were shoulder function 5 6 and pain (Constant Murley Score and Disabilities of the Arm, Shoulder, and Hand or 7 DASH score). Each variable was measured by a blinded physiotherapist at baseline and 8 at one month follow-up.

9 The intervention consists of the use of the eFisioTrack platform in the experimental group to perform active exercises as part of their shoulder rehabilitation. These were performed 10 independently by each patient in a hospital room, using the efisioTrack system without 11 supervision by the physiotherapist. The design and use of eFisioTrack has been assessed 12 for usability and was described as appropriate and technically feasible. The subjects will 13 14 be previously instructed in the use of the system in two 20-minute sessions. The type of 15 exercise and its parameters will be chosen and progressed considering the functional status of the patient and being similar to those executed under the physiotherapist's 16 17 supervision.

18

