15 STATISTICAL ANALYSIS

Descriptive data will be presented as a mean and standard deviation for continuous variables. For statistical analyses, the normality of the data distribution will be assessed by the Shapiro-Wilk test. To compare differences between groups in the studied variables, the Student's t-test will be used for normally distributed data. For each group, a paired ttest will be used to compare baseline and follow-up scores, and the 95% confidence interval (CI) will be calculated for the mean differences.

The theoretical sample size based on a 10-point difference (10%) in the DASH between the two studied groups, assuming a 95% confidence interval, 80% statistical power and 24 20% sampling error, resulted in 36 patients in each group.

25 All analyses will be conducted using SPSS Statistical Package for Windows, version 25

26 (SPSS Inc., 2009, Chicago, Illinois, USA). The significance level was set at P < 0.05.

27

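### The between-group t-test ignores surgical status and baseline DASH in a mixed pilot of 20 to 40, which can cost precision and leaves the SD for an adjusted large trial unreported

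*Combined protocol and SAP*

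**What the plan says.** Study Design, on the study population, admits adults who "suffer a traumatic or degenerative shoulder injury, with or without surgical" treatment, with no quota or cap. On sample size, the same section says the pilot should "have an estimate of standard deviation, which will be used in the sample size calculation" for the large-scale trial, and concludes: "That is why the sample size could be between 20 and 40 participants".

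Allocation is described in Methodology. After the baseline examination, "patients will be randomly assigned to either" supervised exercise or eFisioTrack. A code based on ID digits "was assigned to each participant using a computerized application", a web randomiser. No strata, blocks or minimisation are named.

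Outcome Measures makes DASH primary, places the baseline measurements before randomisation, and treats differences above 10 points as clinically relevant.

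Statistical Analysis says that, between groups, "Student's t-test will be used for normally distributed data". Each group also has a paired t-test of baseline against follow-up. No covariate is named. A theoretical size of 36 per group for a 10-point DASH difference is given without an SD.

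**The concern.** Surgical status is part of how a patient comes to be eligible, and baseline DASH is measured before allocation. Either could predict DASH at one month, and neither costs anything extra to obtain. A t-test with no covariates leaves whatever they explain in the error term.

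Two things are at stake. First, with 10 to 20 patients per arm, the arms can differ noticeably in surgical mix, and the planned analysis cannot account for it when the single result is read. Second, the pilot is meant to supply an SD. The raw SD alone suits a large trial analysed without covariates. It does not suit one that adjusts, and the plan as written would not yield the figure that an adjusted trial needs.

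**Working it through.** **Inputs from the documents.** Total N of 20 to 40; a 10-point DASH target; 95% confidence; 80% power; 36 per group.

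**Inputs assumed, because the documents do not give them.** Equal arms; surgical share p = 0.5 (0.3 as a check); total DASH SD of 15; surgical versus non-surgical difference in mean one-month DASH, D = 5 to 20 points.

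**Step 1: the plan's own figure.** With two-sided alpha 0.05, n per group = 2(1.96 + 0.842)² × SD² / 10². At SD 15 this is 2 × 7.85 × 225 / 100 = 35.3, so 36. An SD of 15 therefore fits the stated figure, but it is not the only reading. A two-sided test at SD 13.5 with 20% dropout gives 37, and a one-sided test at SD 15 with 20% dropout gives 35. The SD of 15 remains an assumption.

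**Step 2: chance imbalance.** With a fixed equal split, the number of surgical patients in one arm is hypergeometric.
- N=20, 10 surgical: a gap of 4 or more means at most 3 or at least 7 in one arm. Probability = 2 × (1 + 100 + 2,025 + 14,400) / 184,756 = 0.179.
- N=40, 20 surgical: a gap of 4 or more means at most 8 or at least 12 in one arm. Probability = 0.343.
- With p = 0.3 the two probabilities are 0.141 and 0.301.

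**Step 3: shift in the group difference.** Shift = (gap / patients per arm) × D. A gap of 4 gives 4/10 × D = 0.4D at N=20 and 4/20 × D = 0.2D at N=40.

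**Step 4: precision and planning SD.** Share of variance due to surgery = p(1 − p)D² / SD². Within-stratum SD = 15 × √(1 − share). SE ratio = √(1 − share). The last column puts the within-stratum SD into the Step 1 formula.

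| D | Shift, N=20 | Shift, N=40 | Variance share | Within-stratum SD | SE ratio | n per group, adjusted (unadjusted: 36) |
|---|---|---|---|---|---|---|
| 5 | 2 | 1 | 2.8% | 14.79 | 0.986 | 35 |
| 10 | 4 | 2 | 11.1% | 14.14 | 0.943 | 32 |
| 15 | 6 | 3 | 25.0% | 12.99 | 0.866 | 27 |
| 20 | 8 | 4 | 44.4% | 11.18 | 0.745 | 20 |

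With p = 0.3 the shares are 2.3%, 9.3%, 21.0% and 37.3%, and the adjusted n is 35, 33, 28 and 23.

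These figures concern surgery alone. The contribution of baseline DASH, and its overlap with surgery, cannot be computed from the documents.

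**The case against.** - **Bias.** A reader might infer that unstratified allocation biases the comparison. It does not. Randomisation keeps the estimate unbiased on average, and the t-test's standard error already includes this variation. At SD 15 that standard error is 15 × √(2/10) = 6.7 at N=20 and 15 × √(2/20) = 4.7 at N=40. The typical (root-mean-square) imbalance at D=15 gives a shift of about 3.4 and 2.4 points. A gap of 4 or more is a minority event.
- **Inflated SD.** A reader might infer that the pilot SD is inflated and the large trial will be oversized. The documents do not support this. Nothing in them shows that surgery predicts DASH. If the large trial keeps the same mix and an unadjusted t-test, the pooled SD is the right input and the smaller residual SD would undersize it. The mismatch arises only if that trial adjusts.
- **Pilot noise.** The 95% interval for an SD runs from about 0.76 to 1.48 times the estimate with 18 degrees of freedom, and 0.82 to 1.29 with 38. At D=15 the pooled SD exceeds the within-stratum SD by a factor of 15/12.99 = 1.15, which is inside both. This limits the practical importance of the SD point. It is no reason to withhold the second figure.
- **Overlap and choice of factor.** Baseline DASH may absorb much of any surgical effect, and the documents do not rank surgery above cause of injury or age. Both points stand. The remedy therefore includes baseline DASH and does not rely on surgery alone.
- **Allocation.** Allocation after the baseline examination is already planned, so that is not a gap. Stratifying in very small blocks has its own price. Guessing the under-represented arm is right about 75% of the time in blocks of 2 and 71% in blocks of 4, against 50% under simple randomisation. Staff at this single site can see which room a patient uses.

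What remains is that two variables known before randomisation go unused in the between-group comparison, which the stated main aim requires.

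**Conclusion.** The point holds as a matter of precision and of matching the SD to its use. The possible gain from adjusting for surgery runs from negligible (SE lower by about 1% at D=5) to substantial (about 25% at D=20), under an assumed total SD of 15 and a half-surgical sample. D, the SD and the surgical share are all unstated, so no single value can be called the expected one. The imbalance probabilities of 18% and 34% assume equal arms and a 50% surgical share; at 30% surgical they are 14% and 30%.

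The documents do not support a claim of bias, of an SD that is certainly too large, or of a large trial that will certainly be oversized. The change is still worth making: its cost is small and known, and reporting both SDs serves the large trial whichever analysis it adopts.

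**What to change.** In Statistical Analysis, replace the between-group t-test for the primary outcome with a linear model (ANCOVA) of one-month DASH on group, baseline DASH and surgery (yes/no), and report the adjusted difference with its 95% confidence interval. Report surgical status by arm. Report both the raw SD of DASH and the model's residual SD, and state that the large trial will use the one that matches its planned analysis.

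The cost is two degrees of freedom: with complete follow-up, residual degrees of freedom fall from 18 to 16 at N=20 and from 38 to 36 at N=40. No eligibility rule, treatment or visit changes, and this part applies even if allocation has begun.

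If allocation has not started, stratifying the list by surgery is an optional addition. Very small blocks should then be avoided, because staff at the site can see the arms.

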19 OUTCOME MEASURES

The baseline measures will be collected before randomization and the outcome assessments will blind. All assessment measures, will be collected by the same clinician who was not involved in the treatment programs. In addition, at the physiotherapy service patients received a paper copy of the questionnaires to fill out on their own.

The following patient-reported outcome measures were used to assess participants' shoulder pain and function: the Disabilities of Arm, Shoulder and Hand (DASH) score and the Constant-Murley (CM) score.

27 • Primary outcome measures

The DASH was taken as a primary outcome measure. It is one of the most widely used self-reported questionnaires that measures symptoms and degree of function related to a disorder in the upper extremity. It has been validated in Spanish and comprises 30 items: 21 about physical function, 6 for symptoms, and 3 to assess social aspects. In addition, there are two optional modules, each with four items, which are used to assess symptoms and function in those whose functional demands are not included in the main part of the questionnaire.

This instrument has been used in previous studies involving physical therapy and exercise for shoulder injuries. It is scored in two components: first the symptom questions (30 items) and second the optional modules. The assigned values for all completed responses are summed and averaged, producing a score that is then transformed on a scale of 0 to 100 by subtracting one and multiplying by . A higher score indicates greater disability. Differences in scores are considered clinically relevant (minimum clinically important difference or MCID) when they are above 10 points.

42 • Secondary outcome measures

The CM score is a commonly used specific instrument for assessing the shoulder joint.
The maximum score is 100 points, 90 to 100 being excellent, 80 to 89 good, 70 to 79

1 medium, and less than 70 poor, considering that the scores can vary with age. This tool 2 includes a subjective assessment of the patient's pain and ability to perform daily 3 activities (35 points) and an objective assessment of mobility and strength by physical 4 examination (65 points). Its use has been specifically validated in shoulder arthroplasty, 5 rotator cuff repair, adhesive capsulitis, and fractures of the proximal humerus, but not in 6 shoulder instability.

7

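### Feasibility is called the main objective and justifies 20 to 40 participants, but other sections state clinical effect as the aim, and the feasibility rates are neither defined nor analysed

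*Combined protocol and SAP*

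**What the plan says.** The combined protocol and SAP gives two answers to what the study is for.

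- **STUDY DESIGN, sample-size paragraph:** "The main objective of this study is to know whether a clinical trial will be feasible and to have an estimate of standard deviation". The SD is meant for sizing a later large-scale trial. The paragraph also names three rates: eligible people willing to take part, then "of participants who drop out of the trial, or of participants who comply with the assigned intervention". It concludes: "That is why the sample size could be between 20 and 40 participants".
- **PROJECT SUMMARY and OBJECTIVES:** "The main aim of the study was to evaluate the effect on clinical variables of monitoring exercises". OBJECTIVES does not mention feasibility.
- **RATIONALE AND BACKGROUND INFORMATION:** "Therefore, the aim of this pilot study was to evaluate the effect on clinical variables of monitoring exercises".
- **OUTCOME MEASURES:** "The DASH was taken as a primary outcome measure". Constant-Murley is the only secondary outcome.
- **STATISTICAL ANALYSIS:** means and SDs, Shapiro-Wilk, between-group and paired t-tests, 95% intervals for mean differences, and significance at P < 0.05. It also gives a sample size, labelled theoretical, of 36 per group for a 10-point DASH difference at 80% power.

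**The concern.** A pilot's main objective should lead to its outcomes, its analysis and its size. Here the size follows from one objective, while the outcomes and analysis follow from another.

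If feasibility governs, the plan leaves out the collection and analysis of rates that it names as part of its main objective. It also does not say what result would make a large trial feasible. Eligible patients who are not logged during recruitment, and sessions that are not counted, may not be recoverable afterwards.

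If clinical effect governs, a comparison tested at P < 0.05 rests on 20 to 40 patients, beside a calculation in the same document that asks for 72. A non-significant result could then be misread as showing that unsupervised exercise with the platform matches supervised exercise.

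**Working it through.** **1. What is planned for each feasibility quantity**

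| Quantity | Collection | Analysis |
|---|---|---|
| SD | DASH at baseline and one month | Mean and SD planned |
| Dropout | Not defined; can be counted from those randomised and those assessed at one month | None stated |
| Willingness | Signed consent (ETHICAL ASPECTS) gives the numerator; the referral period and eligibility criteria give a frame; no log of eligible patients is planned | None stated |
| Compliance | No definition; no session record planned in either arm | None stated |

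On compliance, the only session count in the documents is for training: experimental patients will "be previously instructed in the use of the system in two 20-minute sessions". The background says that the platform "could be used to monitor patients' activity in the scheduled exercise sessions", so experimental-arm data may exist. No section plans to keep or use them, and they would not cover controls.

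So two of the four quantities can be obtained from what is planned, and two have no planned collection.

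**2. The plan's own 36 per group**

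Inputs from STATISTICAL ANALYSIS: difference 10, 80% power, 5% significance. Assumptions: two-sided test, equal arms, and an SD, because none is given.

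n per group = 2 × (1.960 + 0.842)² × SD² / 10²

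With SD 15: 2 × 7.849 × 225 / 100 = 35.3, rounded up to 36. The exact t-test has 79.7% power at 36. Solving for SD instead: 10 × √(36/2) / 2.802 = 15.1. SD 15 is therefore what the plan's figure roughly implies, not independent evidence. With SD 20 the same formula gives 63 per group.

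**3. What 20 to 40 gives for the clinical comparison**

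Power is from the exact two-sample t-test for 10 points, with none lost. The 95% half-width is t × SD × √(2/n), with n per arm.

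| Total (per arm) | Power, SD 15 | Power, SD 20 | Half-width, SD 15 |
|---|---|---|---|
| 20 (10) | 29% | 19% | 2.101 × 15 × √(2/10) = 14.1 |
| 40 (20) | 54% | 34% | 2.024 × 15 × √(2/20) = 9.6 |
| 72 (36) | 80% | 55% | 1.994 × 15 × √(2/36) = 7.1 |

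OUTCOME MEASURES sets the minimum clinically important difference at 10 points. With 20 patients, an observed difference of zero would not exclude it in either direction (−14.1 to 14.1). With 40 it would only just do so (−9.6 to 9.6).

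**4. What 20 to 40 gives for the feasibility quantities**

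- Pooled SD, 95% interval as a multiple of the estimate, √(df/χ²): 0.76 to 1.48 at 20 (df 18) and 0.82 to 1.29 at 40 (df 38).
- A by-arm rate, for example 8 of 10 compliant: 49% to 94% (Wilson) or 44% to 97% (exact). The 80% is illustrative.

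**The case against.** - **The list of rates is loosely worded.** It joins its items with an or, so it may be a list of what such a pilot might estimate and not a commitment to all three. That is a fair reading. But the paragraph puts the rates under its main objective and rests the size on them, and not one is carried into the outcomes or analysis.
- **A reader might infer that willingness and compliance cannot be estimated.** The documents do not support that. There is a referral frame, consent is signed, and patients exercise in hospital, either supervised or on a platform that may record activity. What stands is that no collection is described in the supplied text.
- **A reader might infer that this pilot was meant to enrol 72 and falls short.** That is also unsupported. The 36 per group is labelled theoretical, the SD is wanted for a large-scale trial, and the sample-size paragraph gives 20 to 40 for this study. What stands is narrower: the calculation sits in this study's analysis section beside significance tests, and no sentence says that it does not apply here.
- **The power figures are secondary.** They matter only if clinical effect governs, and they rest on an SD back-solved from the plan's own number. Both points are right. The contradiction in objectives does not depend on them.

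**Conclusion.** The concern holds in this form. The document states two different main objectives. The one that justifies the size names rates that are not defined, analysed or, for willingness and compliance, given any planned collection. It also carries a size and power that 20 to 40 participants do not meet, without separating them from this pilot.

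If clinical effect governs, power for 10 DASH points is 29% to 54% at SD 15 and 19% to 34% at SD 20, with a 95% half-width of 14.1 to 9.6 points at SD 15. These figures assume equal arms, a two-sided 5% test and no losses.

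The finding does not show that 20 to 40 is wrong for a feasibility study or that the rates are out of reach. Statements about what is absent cover the supplied text only.

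**What to change.** **In either case**

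1. State one main objective, in the same terms, in PROJECT SUMMARY, RATIONALE AND BACKGROUND INFORMATION, OBJECTIVES and STUDY DESIGN. The choice is the sponsor's; feasibility fits the title and the size.
2. State in STATISTICAL ANALYSIS that 36 per group and 80% power are not this pilot's size or power.

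**If feasibility is the objective**

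3. Add three proportions with 95% intervals to OUTCOME MEASURES and STATISTICAL ANALYSIS: willingness (consented/eligible, from a screening log), dropout (by arm) and compliance (a sponsor-set definition, from session counts in both arms; platform records may serve the experimental arm if kept).
4. Set in advance a sponsor-chosen criterion for judging a large trial feasible.
5. Report between-group DASH and Constant-Murley differences as estimates with 95% intervals, not as a test of efficacy.

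**If clinical effect is the objective**

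6. Reword the sample-size paragraph so that feasibility is not the main objective, and state the power that 20 to 40 gives under a stated SD.

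**Optional:** say which DASH SD is meant (baseline, follow-up or change) and give its 95% interval.

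**Cost:** text edits and, under feasibility, a screening log and per-patient session counts. By-arm rates will be imprecise. The protocol is dated 18 July 2023 and recruitment is planned from July 2023, so a log started after recruitment opens misses patients already screened.

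### The plan says every outcome is measured by a blinded physiotherapist, but the primary outcome, DASH, is self-reported by patients who know their arm

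*Combined protocol and SAP*

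**What the plan says.** **Blinding.** The Project Summary (Methods), Study Design and Methodology sections each name two outcomes, the Constant-Murley score and DASH. Each then applies one statement to both. In Methodology it reads "Each variable was measured by a blinded physiotherapist at baseline"; in Study Design each variable is to be "measured by a blinded physiotherapist at baseline and at one month follow-up". Outcome Measures adds, without qualification, that the outcome assessments will be blind, and that "All assessment measures, will be collected by the same clinician who was not involved in the treatment programs". The trial is described as single blind, and the assessing physiotherapist is the only party named as blinded.

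**The primary outcome.** Outcome Measures states "The DASH was taken as a primary outcome measure" and places it among the "self-reported questionnaires that measures symptoms and degree of function". It also says that, at the physiotherapy service, "patients received a paper copy of the questionnaires to fill out on their own". Baseline measures are collected before randomisation.

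**What patients can see.** Exercises are done "supervised by the physiotherapist (control group) or in a separate room without therapist" supervision (experimental group). Methodology adds that subjects are trained on the system in two 20-minute sessions. No masking of patients is described.

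**The concern.** Blinding an assessor protects an outcome only so far as the assessor forms the judgement. For a self-completed questionnaire the patient forms it, and here the patient knows how he or she was treated. The plan therefore gives its primary outcome a safeguard that the outcome does not have.

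What is at stake is the claim the trial can make. A report that followed the Methodology wording would present the DASH comparison as a blinded-assessor result. A reader would then discount the possibility that patients answered differently because they had, or lacked, a therapist beside them. Objectives makes the effect on clinical variables the main aim, and Statistical Analysis specifies between-group t-tests at P < 0.05, so this comparison is likely to be read as evidence.

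**Working it through.** No figure in the plan bears on this point, so the check sets the sections side by side.

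1. **Who is said to measure DASH?** The Project Summary, Study Design and Methodology say a blinded physiotherapist. The statement covers each variable, and DASH is named in the sentence before it.

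2. **Who produces the DASH answers?** By Outcome Measures, the patient. The instrument is self-reported and patients fill in the questionnaires themselves. All 30 items (21 function + 6 symptoms + 3 social = 30) come from that source.

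3. **Does the patient know the arm?** The plan does not say so outright, but it follows from how the arms are delivered. One arm has a therapist present. The other works alone in a separate room with a device the patient was trained to use.

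4. **At which visit does this matter?** Write the one-month score reported in an arm as F + r, where F is the score that would be given without knowledge of the arm and r is any shift due to that knowledge. Let B be the baseline score, E the experimental arm and C the control arm. Baseline precedes randomisation, so B carries no such shift. Then:
   - Difference at one month: (F_E + r_E) − (F_C + r_C) = (F_E − F_C) + (r_E − r_C).
   - Difference in change: (F_E + r_E − B_E) − (F_C + r_C − B_C) = [(F_E − B_E) − (F_C − B_C)] + (r_E − r_C).

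   The same term, r_E − r_C, enters both. Subtracting baseline does not remove it, and blinding the clinician who handles the form does not change it. The documents give neither its size nor its sign.

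5. **Where can assessor blinding work?** Outcome Measures splits the Constant-Murley score into 35 points for the patient's own view of pain and daily activities and 65 points for mobility and strength by physical examination (35 + 65 = 100). Assessor blinding can act on the 65. The 35 are subjective and share the limitation of DASH.

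The blinding statement is thus attached to both outcomes but can hold for only part of the secondary one.

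**The case against.** **The protocol never claims patient blinding.** This is correct. It says single blind and names only the assessor, and supervised versus unsupervised exercise cannot readily be masked from patients. The point does not ask for patient blinding. It is because patients are unblinded that the statement cannot extend to a patient-reported primary outcome.

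**Outcome Measures already describes DASH as self-completed.** Largely so, and this keeps the correction small. But that section also says without qualification that assessments will be blind, and three other sections say a blinded physiotherapist measures each variable. No section states the limitation.

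**It is a pilot.** The sample-size paragraph in Study Design gives feasibility, a standard deviation and participation rates as the main objective, with 20 to 40 participants. This lowers the weight of any bias in a between-group P value. It does not remove the point, given the stated clinical aim and the planned tests.

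**A stronger reading: two raters, or two DASH records.** The sentence on the paper copies is worded as an addition to the clinician's collection of the measures. A reader might infer that each patient has both a clinician-administered and a self-completed DASH, with the choice between them left open. The documents do not support this. No section describes a clinician-administered DASH. Collection by the clinician most naturally means gathering the forms and performing the Constant-Murley examination. The analysis text does not help that reading either: it refers to the studied variables in general, and DASH appears in Statistical Analysis only in the sample-size sentence.

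**A second stronger reading: a quantified rise in false positives.** Any such figure would need a DASH standard deviation and a reporting shift, and the documents give neither. It would also describe a bias that the correction discloses but does not remove.

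**Conclusion.** The point holds as an error in a stated property of the primary outcome: DASH is not measured blind at one month, although four sections say or imply that it is. Baseline DASH is not affected.

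In extent, none of the 30 DASH items and at most 65 of the 100 Constant-Murley points can be protected by assessor blinding. The size and direction of any resulting bias in the between-group DASH difference cannot be derived from the documents.

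The conclusion rests on one inference, that patients know their arm, which follows directly from how the two arms are delivered. It does not rest on there being more than one DASH record or rater. The wording should be corrected because doing so is nearly free and changes what the trial may claim. Nothing here requires a change of design.

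**What to change.** - In the Project Summary, Study Design, Methodology and Outcome Measures sections, limit the blinded-assessment statement to the examiner-rated part of the Constant-Murley score (the 65 points by physical examination).
- In Outcome Measures, state that the primary DASH is the patient-completed paper form at both baseline and one month, and that the clinician only hands it out and collects it.
- State that the between-group DASH difference will be reported and interpreted as self-report by unblinded participants.

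The cost is protocol wording only, with no extra data, visits or staff. The downside is that the trial can no longer describe its primary outcome as blinded. Any reporting bias in DASH remains, but it will be disclosed.
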